5.3 LIFESTYLE CONSIDERATIONS

5.3.1 STANDARD TREATMENT RECOMMENDATIONS

Standard of care (SOC) recommendations prepared by the GpCRC Steering Committee for the management of patients with gastroparesis or related disorders cover these broad categories as follows:

- Standardized set of recommendations on following a Gastroparesis diet.
- Recommendations on the use of pain medications and to eliminate drugs that might exacerbate the underlying dysmotility disorder or prevent the beneficial actions of a prokinetic.

These recommendations will be included in the BESST Standard of Care Standard Operating Procedures (SOP) and will be provided to each participant.

Also, during the BESST study, participants are asked to:

- Refrain from consumption of alcohol, grapefruit or grapefruit juice, pomelos, exotic citrus fruits, grapefruit hybrids, and fruit juices until after the final dose.

These guidelines are given in the investigator's brochure for buspirone and are included due to possible alteration of p450 degradation pathways.

5.4 SCREEN FAILURES

Screen failures are defined as participants who consent to participate in the clinical trial but are not subsequently randomly assigned to a study treatment group. A minimal set of screen failure information is required to ensure transparent reporting of screen failure participants, to meet the Consolidated Standards of Reporting Trials (CONSORT) publishing requirements, and to respond to queries from regulatory authorities. Minimal information includes demographics, reason for screen failure, and any serious adverse event (SAE). Screening failures also include participants who meet medical eligibility criteria but change their mind and do not consent to randomization into the trial. We collect all of the above information on each screen failure using a case-report form keyed into the BESST database.

Individuals who do not meet the criteria for participation in this trial (screen failure) because of a contraindicated medication or who is unable to complete all tests within the allotted screening window may be rescreened one time. A rescreened participant is assigned the same participant number as for the initial screening.

5.5 STRATEGIES FOR RECRUITMENT AND RETENTION

5.5.1 RECRUITMENT

Approximately 108 participants will be recruited from the six clinical centers of the GpCRC (averaging 18 participants per center) over a 30-month period. Participants will be recruited from outpatient clinics and inpatient hospital settings.

Potentially eligible participants will be identified and registered for screening at the participating clinical centers subject to the inclusion and exclusion criteria listed above. Eligible and consenting participants will be randomized to a treatment group after completion of all required screening procedures, keying of all required data elements into the data system, and passing eligibility checks for the BESST trial.

Each clinical center will develop a specific recruitment plan. These plans will vary from clinic to clinic depending on the available pools of participants and local recruitment resources. Clinics will attempt to recruit sufficient overall

numbers of minorities and males since gastroparesis is reported to be rare in African-Americans and infrequent in men, so that the study results can be generalized to these sub-groups of the U.S. population.

Participants may be reimbursed for travel expenses for each visit completed depending on each clinic's resources.

[figure not shown]
6 STUDY INTERVENTION

6.1 STUDY INTERVENTION(S) ADMINISTRATION

6.1.1 STUDY INTERVENTION DESCRIPTION FROM FDA PACKAGE INSERT

Buspirone hydrochloride tablets, USP is an antianxiety agent that is not chemically or pharmacologically related to the benzodiazepines, barbiturates, or other sedative/anxiolytic drugs. Buspirone hydrochloride is a white crystalline, water soluble compound with a molecular weight of 422.0.

Chemically, buspirone hydrochloride is 8-[4-[4-(2-pyrimidinyl)-1piperazinyl]butyl]-8-azaspiro[4.5]decane- 7,9-dione monohydrochloride. The empirical formula C₂₁H₃₁N₅O₂ • HCl is represented by the following structural formula:

The mechanism of action of buspirone is unknown. Buspirone differs from typical benzodiazepine anxiolytics in that it does not exert anticonvulsant or muscle relaxant effects. It also lacks the prominent sedative effect that is associated with more typical anxiolytics. In vitro preclinical studies have shown that buspirone has a high affinity for serotonin (5-HT 1a) receptors. Buspirone has no significant affinity for benzodiazepine receptors and does not affect γ -aminobutyric acid (GABA) binding in vitro or in vivo when tested in preclinical models.

Buspirone has moderate affinity for brain D2-dopamine receptors. Some studies do suggest that buspirone may have indirect effects on other neurotransmitter systems. Buspirone is rapidly absorbed in humans and undergoes extensive first-pass metabolism. In a radiolabeled study, unchanged buspirone in the plasma accounted for only about 1% of the radioactivity in the plasma. Following oral administration, plasma concentrations of unchanged buspirone are very low and variable between subjects. Peak plasma levels of 1 ng/mL to 6 ng/mL have been observed 40 to 90 minutes after single oral doses of 20 mg. The single-dose bioavailability of unchanged buspirone when taken as a tablet is on the average about 90% of an equivalent dose of solution, but there is large variability.

The effects of food upon the bioavailability of buspirone have been studied in eight subjects. They were given a 20 mg dose with and without food; the area under the plasma concentration-time curve and peak plasma concentration (C_{max}) of unchanged buspirone increased by 84% and 116%, respectively, but the total amount of buspirone immunoreactive material did not change. This suggests that food may decrease the extent of presystemic clearance of buspirone.

Buspirone is a 5-HT 1 receptor agonist that is FDA approved for the treatment of anxiety. It is an anxiolytic psychotropic drug of the azapirone chemical class, used primarily to treat generalized anxiety disorder. Unlike most drugs predominantly used to treat anxiety, buspirone's pharmacology is not related to benzodiazepines or

barbiturates, and so does not carry the risk of physical dependence and withdrawal symptoms for which those drug classes are known. The proximal gastric fundus tone is mediated by a balance of excitatory cholinergic and inhibitory non-adrenergic, none-cholinergic neural input. Recently, 5-HT 1a receptor expression has been reported in the myenteric plexus of the GI tract including the stomach (66). Buspirone was effective in relaxing the gastric fundus via 5-HT 1 receptor pathway in both in vitro and in vivo experimental models using guinea pigs.

6.1.2 DOSING AND ADMINISTRATION

In this trial, a 10 mg buspirone tablet will be over encapsulated in a size 0 gelatin capsule (approximately 2.2 cm) with partial filler, the inactive ingredients being: colloidal silicon dioxide, lactose, magnesium stearate, microcrystalline cellulose, and sodium starch glycolate. The matching placebo capsule will contain only filler. Each bottle contains 120 capsules.

The random treatment assignment will consist of a numbered study drug bottle; each bottle number will be unique and each participant will be assigned a specific bottle number. The bottle number issued by the randomization program will correspond to numbered bottles of study drugs which have been sent to the clinical center's research pharmacy by the SDRC's GMP Research Pharmacy. Upon learning the bottle number to be issued to the specific participant, the research pharmacy will issue that bottle to the participant. Each participant's random treatment assignment will be generated for that specific participant and will not be transferable to another participant. Once the assignment has been generated, the participant will be issued the study drug and instructed about taking the study drug orally 30 minutes before meals every day and monitoring for potential adverse effects. The study drug dispensed at the time of randomization will be a bottle containing either over-encapsulated 10 mg tablets of buspirone or identical looking placebo capsules.

Participants will receive an **Information for Patients** document with their study medication. This document will instruct the participant as follows:

1. Do not take a monoamine oxidase inhibitor (MAOI). Ask your healthcare provider or pharmacist if you are not sure if you take an MAOI, including the antibiotic linezolid.
2. Do not take an MAOI within 2 weeks of stopping buspirone unless directed to do so by your physician.
3. Do not start buspirone if you stopped taking an MAOI in the last 2 weeks unless directed to do so by your physician.
4. Inform your Primary Care Physician that you are participating in a randomized, controlled trial comparing buspirone hydrochloride (10 mg 3 times per day) and placebo.
5. Inform your physician and the study investigator about any prescription or non-prescription medications, prescription or non-prescription supplements, alcohol, or drugs that you are now taking or plan to take during your participation in BESST.
6. Inform your physician if you are pregnant or breastfeeding, or if you are planning to become pregnant, or if you become pregnant while you are taking buspirone hydrochloride tablets.
7. Until you experience how this BESST study medication affects you, do not drive a car or operate potentially dangerous machinery.
8. During your treatment with BESST study medication, avoid consumption of grapefruit juice or eating grapefruit, pomelos, exotic citrus fruits, grapefruit hybrids, or fruit juices until after the final dose.
9. If you miss a dose of this medicine, take it as soon as possible unless it is almost time for your next dose, in which case, skip the missed dose and go back to the regular dosing schedule. Do not double doses.

6.2 PREPARATION/HANDLING/STORAGE/ACCOUNTABILITY

6.2.1 ACQUISITION AND ACCOUNTABILITY

An investigator may not administer an investigational new drug to human subjects until the IND goes into effect (30 days after IND receipt by FDA) or sooner if notified. After review by the FDA, the use of buspirone in the BESST trial was given an IND exempt status. All masked drug and placebo bottles will be distributed to the individual GpCRC Clinical Centers' Investigational Pharmacies or responsible entities by the SDRC's contracted GMP Drug Distribution Center according to the directions of the SDRC. The GMP Drug Distribution Center will purchase the study drug (buspirone) and the materials needed for manufacturing the placebo capsules, over-encapsulating the buspirone capsule, manufacturing the microcrystalline powder contained in the matching placebo capsule, encapsulating the placebo capsule, bottling the active and placebo capsules individually, labeling bottles according to the SDRC directions, and shipping the drugs to the clinics. Expired and returned study drug will be disposed of by each clinical center after authorization from the SDRC.

The local Investigational Pharmacy will provide the clinic investigator or coordinator with a masked BESST study drug bottle upon request after the participant's randomization. The SDRC provides the bottle number to be requested from the local pharmacy after the randomization request by the clinic. Participants will be dispensed a bar-coded medication bottle as labeled by the GMP Research pharmacy: "Buspirone 10 mg or placebo. Take one capsule orally 3 times per day, 30 minutes prior to meals."

Participants are instructed to take a single capsule of 10 mg buspirone or placebo three times a day, approximately 30 minutes prior to meals.

Drug accountability information is maintained by the GMP Research Pharmacy, the local clinic investigational pharmacy, and in the study database for adjudication coordinated by the SDRC at the end of the trial or at any time during the trial, as needed.

6.2.2 FORMULATION, APPEARANCE, PACKAGING, AND LABELING

Buspirone hydrochloride is supplied by several pharmaceutical manufacturers and will be purchased by the SDRC's GMP Research Pharmacy, and then over-encapsulated in a gelatin capsule for oral administration. Half the capsules will contain 10 mg buspirone hydrochloride, USP (equivalent to 9.1 mg of buspirone free base, respectively). The buspirone tablets contain the following inactive ingredients: colloidal silicon dioxide, lactose, magnesium stearate, microcrystalline cellulose, and sodium starch glycolate. The other half of the gelatin capsules (placebo) will contain only the filler.

6.2.3 PRODUCT STORAGE AND STABILITY

Store at 20° to 25°C (68° to 77°F) [See USP Controlled Room Temperature].

Dispense in a tight, light-resistant container as defined in the USP, with a child-resistant closure (as required).

6.2.4 PREPARATION

No preparation is required because capsules will be provided to sites in participant ready packaging.

6.3 MEASURES TO MINIMIZE BIAS: RANDOMIZATION AND BLINDING

Randomization: The randomization scheme will assign participants in randomly permuted blocks of assignments stratified by clinical center. This scheme will ensure that the two groups will be of nearly equal size and will be balanced by calendar time of enrollment to ensure equal numbers of participants by time of enrollment (to minimize secular effects) and by clinic (to minimize clinic effects).

The randomization plan will be prepared and administered centrally, using a secure web application, by the SDRC. An assignment will be issued only if the trial database shows that the participant is eligible, has signed the consent statement, and has had all required baseline data keyed to the data system.

Treatment assignments are double-masked throughout the study until all data collection for the BESST trial has been completed, i.e., after completion of the 2-week post-trial follow-up visit for all participants. Every effort will be made to maintain the masking throughout the study except in emergency situations. The randomization code masking the bottle contents will not be provided by the SDRC without the knowledge of the clinical center's principal investigator.

Unmasking of study medication will occur under the following conditions:

- **Severe allergic reaction (Stevens-Johnson Syndrome):** Study medication is stopped indefinitely. The participant, primary care provider (PCP), and the investigator will be unmasked.
- **Pregnancy during the study:** Study medication will be stopped indefinitely, and the coded medication will be unmasked. The participant, PCP, and investigator will be notified of the assigned treatment and the associated risks of teratogenicity.

In unforeseen situations where the clinical center principal investigator considers unmasking is in the best interest of the participant's health and well-being, unmasking may be done after notifying the Executive Committee. The Data and Safety Monitoring Board will review all instances of unmasking that have occurred.

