8.1.4 FOLLOW-UP VISITS

Participants will return to the clinical center for follow-up visits at 2 and 4 weeks. A post-treatment washout phase visit will occur at week 6. Each visit will have an interval of time surrounding the ideal date for the visit during which the visit may be done and the data included in the trial database. The ideal date for the week 2 visit is the randomization date plus 2 weeks (14 days); the ideal date for the week 4 visit is the randomization date plus 4 weeks (28 days). Visit windows will be constructed to be contiguous, so that at any point in time, some visit window is open, subject to a check on the minimum separation of at least one week between consecutive visits. The specific assessments and procedures required at each of the follow-up visits are:

- **Week 2:** pregnancy test for females of child bearing potential, follow-up medical history with review of adverse events, concomitant medications and study adherence, assessment of vital signs (systolic and diastolic blood pressure, heart rate, respiratory rate, body temperature), and the following surveys: Hospital anxiety and depression (HADS), PAGI-SYM, and the Clinical Patient Grading Assessment Scale (CPGAS)([see section 8.1.5](#)) and a symptoms side-effect questionnaire (see [section 8.2](#) for details). In addition, the participant will return their Daily-Diary forms and receive another set to complete for return at the Week 4 visit.
- **Week 4:** the week 4 visit will require two fasting visits scheduled as close together as possible, preferably 1 day apart.
 - The participant will refrain from taking their buspirone the morning of the GES test, and take it 30 minutes prior to the GES test. Information to be collected at this visit includes: pregnancy test for females of child-bearing potential, a GES test, follow-up medical history with review of adverse events and concomitant medications, physical exam and ECG, fasting blood draw for CMP and CBC, review of adherence and the following surveys: HADS, SF-36v2 Quality of Life, PAGI-SYM, GSRS, PAGI-QOL, PHQ-15, symptom side-effects, and the CPGAS. Fasting blood will be drawn for serum and plasma banking. In addition, the participant will return their daily-diary forms and receive one more set of daily-diary forms to complete each night to return at their 6-week visit.

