Analysis of regional intragastric meal distribution will be performed of the digital archived gastric emptying images, both at baseline and at the 4-week visit. We will use a modification of the method reported by Piessevaux, Tack, et al to assess intragastric meal distribution [14]. We will use our semi-automated analysis of regional intragastric meal distribution during GES. The analysis begins by aligning the images, then drawing regions of interest around the stomach using thresholding. The longitudinal axis of the stomach is then constructed. The stomach is then divided into two (proximal, distal) regions of interest by finding the midpoint of the longitudinal axis. The amount of radioactivity in each gastric region will be expressed as a percent of the total amount of radioactivity in the stomach at time 0. This will be assessed over time. The ratio of proximal over distal counts will be computed for each time period (0, 1, 2, 4 hours). The amount in the proximal region of interest at time 0

provides a measure of fundic accommodation. Impaired fundic accommodation using IMD is <0.568 ratio of the proximal gastric counts to the total gastric counts.

Electrogastrogram (EGG) with water load satiety test [36]:

For each EGG and water load test, the clinical center needs to have a one-liter opaque cup for water, 3 EGG leads, a dedicated quiet area for the EGG recording, a reclining chair, a blanket and the 3CPM EGG equipment and software. In addition, if the participant normally takes insulin, then they should take one-half of their normal long-acting insulin dose prior to the visit. The morning of the week-4 EGG, the participant will wait to take their buspirone dose *until 15 minutes before the baseline EGG*.

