9.4.9 EXPLORATORY ANALYSES

Outcomes for exploratory or ancillary analysis, depending on the timeframe of additional work required to interpret and quality control data from the gastric emptying scintigraphy tests and the electrogastrogram test digital scans at the GpCRC central resource centers, are listed below:

The first and second outcomes are ancillary:

1. Changes at 4-weeks in Fundic Accommodation (FA) using digital analyses of the GES test images
2. Changes and mean changes, respectively, at 4-weeks in EGG test gastric rhythm measures and water satiety: a) clinical EGG diagnosis (normal, tachygastria, bradygastria, mixed gastric dysrhythmias; b) percentage time and distribution of power in normal 3 cpm EGG activity before and after the water load satiety test and c) total volume of water ingested.

This following outcome is exploratory since it is using the PRO daily-diary version of the ANMS GCSI questionnaire that is not currently validated; however, these outcomes may provide sensitivity analyses on several secondary outcomes.

3. Mean changes at 4-weeks in each of the 7 items on the ANMS GCSI-DD questionnaire: nausea, postprandial fullness, early satiety, upper abdominal pain, episodes of vomiting, episodes of retching, overall symptom severity, as well as the total core symptom composite score. The average severity scores from the last 7-days of treatment are subtracted from the 7-day average baseline severity scores for each of the items.

These two outcomes listed below are ancillary since they are not necessarily powered to detect a change between treatment groups; however, they may provide information on buspirone to develop further hypotheses in the future.

4. Changes at 4-weeks in each of the 15 symptom severity items measured on the PAGI-SYM instrument not included in secondary outcomes item 3, including retching, lower abdominal pain, lower abdominal discomfort, constipation, and diarrhea
5. Changes at 4-weeks in each of the 5 subscores of the Gastrointestinal Symptom Rating Scale (GSRS).

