10.1.7 CLINICAL MONITORING

Clinical site monitoring is conducted to ensure that the rights and well-being of trial participants are protected, that the reported trial data are accurate, complete, and verifiable, and that the conduct of the trial complies with the currently approved protocol/amendment(s), with International Conference on Harmonisation Good Clinical Practice (ICH GCP), and with applicable regulatory requirement(s).

- Monitoring for this study will be performed by the SDRC of the GpCRC.
- To ensure data quality and reduce data entry error, double-data entry of all data collection forms is required. The SDRC will incorporate into the data entry programs a series of edit checks, including range checks, logic checks (e.g., skip patterns), and consistency checks, both within a data form and across forms. These integral checks are designed to detect deficiencies in the data before they are entered into the study database, so that the deficiencies may be easily and accurately corrected. In addition, the SDRC will perform frequent computerized edit checks on entered data. The SDRC will also perform ongoing comparisons of copies of entered data forms with the databases to ensure that data entered into the data system reflect those recorded on the forms. Such audits will help to pinpoint problems that cannot be detected by computer editing and may be used to guide increased scrutiny when needed. Any data queries identified will be flagged for action by the clinical site until resolved.
- The data system will maintain a clear and complete audit trail of all changes to the study databases. All changes to data forms will be documented appropriately on the paper form and entered into GpCRC BESST data system. All forms entered and/or edited in the data system will be identified by the unique Personal Identification Number (PIN) of the operator, the network address (the "IP" address) of the computer being used, and the date and time of the operation. Records will not be deleted but rather marked as having been superseded. The SDRC will implement various procedures to ensure the quality of its internal operations. These will include the development and maintenance of documentation regarding procedures for receiving, processing, and analyzing data, and duplicated programming for selected procedures to check for errors in software database and analysis systems.

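### Section 6.3 lets masking end at the last week-6 visit, before adverse-event windows, data queries and central GES/EGG readings need be closed

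*Combined protocol and SAP*

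**What the plan says.** **When masking ends.** Section 6.3 (Measures to Minimize Bias) keeps treatment assignments masked "until all data collection for the BESST trial has been completed, i.e., after completion of the 2-week post-trial follow-up visit for all participants". Section 8.1.4 fixes that visit: "A post-treatment washout phase visit will occur at week 6". The SDRC prepares and administers the randomization.

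**What can still be open then.**

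- *Adverse events.* Section 8.3.4 records non-serious events until 7 days, and serious events until 30 days, after the last day of participation. Events are followed until they resolve or stabilize. A clinician judges severity and relationship to study product, and section 8.3.3.2 allows the relationship to be upgraded later.
- *Central readings.* Section 9.4.9 makes the exploratory and ancillary analyses conditional, "depending on the timeframe of additional work required to interpret and quality control data from the gastric emptying scintigraphy tests". EGG recordings, which are also handled centrally, fall under the same condition. Section 9.4.7 includes the baseline fundic accommodation subgroup only if that measure is ready when the primary paper is analysed.
- *Queries.* Section 10.1.7: "Any data queries identified will be flagged for action by the clinical site until resolved". No date or link to unmasking is given.
- *Drug accountability.* Section 6.2.1 holds the records "in the study database for adjudication coordinated by the SDRC at the end of the trial", and the sentence goes on to allow adjudication at any point during the trial.

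**How the readings are made.** Section 8.1.6: "Analysis of regional intragastric meal distribution will be performed of the digital archived gastric emptying images", at baseline and week 4, and "We will use our semi-automated analysis of regional intragastric meal distribution during GES". In section 9.4.9 the EGG outcome includes a categorical clinical diagnosis.

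**The concern.** A masking rule should protect every judgement that enters the analysis data. Section 6.3 ties the end of masking to a visit and equates that visit with complete data, whereas the usual trigger is a locked database. If the rule is applied as written, codes may be opened while clinicians are still grading events and judging relatedness, while sites are still answering queries, and while central readers are still working on images and EGG recordings.

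Three things are at stake:

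- Frequency and severity of adverse events are a secondary outcome (item 14), and relatedness is reported with them.
- Fundic accommodation is described in section 3 as the drug's primary target, so the meal-distribution readings, with the EGG, carry the evidence on mechanism.
- A correction to any data item made after the codes are known invites doubt, even where it is innocent.

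The SDRC administers the randomization, runs the edit checks and audits, and coordinates accountability adjudication. A written lock-before-release rule would normally separate these functions, and the available text has none.

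**Working it through.** The plan gives no figure to reproduce. The check sets the masking rule against the timing of each data stream, with a little calendar arithmetic to bound the exposure.

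**1. Is data collection complete at the last week-6 visit?**

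Inputs: week-6 visit (8.1.4); 7-day and 30-day windows (8.3.4); 108 participants over 131 weeks of recruitment (1.1).

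- Taking week 6 as day 6 × 7 = 42, the last participant's window for non-serious events runs to day 42 + 7 = 49, and for serious events to day 42 + 30 = 72.
- So the equation in section 6.3 of the last visit with the end of all data collection conflicts with section 8.3.4 by up to 30 days.

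**2. How many participants does that touch?** Assume even enrolment and every visit on its ideal day.

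- Rate: 108 / 131 = 0.82 participants per week.
- Inside the 7-day window at the last visit: 0.82 × 7/7 = 0.82, about 1.
- Inside the 30-day window: 0.82 × 30/7 = 3.5, about 4 of 108 (3.5/108 = 3.3%).
- Follow-up to resolution has no end date, so events that began earlier may add to this. The documents do not allow that number to be estimated.

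**3. Can central readings be outstanding?** Yes. Section 9.4.9 leaves their timing open, and section 9.4.7 provides for the case in which baseline fundic accommodation is not ready for the primary paper. The codes are in use by then. The ceiling is 108 × 2 = 216 GES studies and 216 EGG tests, reached only if nothing is read earlier.

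**4. Which readings involve judgement?**

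| Item | Exposure if read late with codes known |
|---|---|
| Meal distribution | Some: semi-automated regions by thresholding, constructed axis and midpoint, numerical cutoff 0.568 |
| Clinical EGG diagnosis | Yes: a categorical reading |
| Percentage time and power at 3 cpm | Little: quantitative signal measures |
| Water volume | Little: recorded in mL at the visit |

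**5. Is there another safeguard?** The available text mentions no database lock or data freeze, no query closure before release, and no masking of GES or EGG readers.

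**6. Is the primary outcome exposed?** The PAGI-SYM subscore is completed by the participant at week 4, two weeks before that participant's final visit. Central reading cannot alter it. Only a query answered or a correction made after release could.

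**The case against.** The strongest reply is that section 6.3 sets a minimum period of masking. It names no release date, and it does not say that site clinicians or central readers will be given the codes. That stands: a reader might infer that the codes are opened on the day of the last visit, and the text does not say so. The point is that the rule permits release before the data are final and nothing else visible prevents it.

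The plan also has real data controls: double entry, edit checks, form-to-database audits, and an audit trail in which records are superseded and never deleted (10.1.7). These make late changes traceable, but they do not make them masked. Nor does an open query process prove that queries will outlast the last visit.

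Recruitment runs for 30 months, so many readings could be finished before the last visit, and semi-automation narrows the reader's discretion. Both limit the exposure without removing it. The IMD and EGG outcomes are labelled ancillary, and section 9.4.1 rests the primary conclusion on the intention-to-treat analysis of a self-reported score. That is fair, and it keeps the point modest.

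Finally, section 10.1.5 (key roles and governance) was not in the text available and might describe the readers. It would not change the explicit wording of section 6.3.

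**Conclusion.** The point holds and is worth correcting. The stated end of masking precedes the end of data collection as section 8.3.4 defines it, and it is not tied to query closure, database lock or completed central readings. The exposure covers late event grading and relatedness, late query resolution, and the judgement-based part of any meal-distribution or EGG reading still outstanding. The event windows involve about 4 participants on the assumptions shown. The number of late readings and queries is unknown, and the size of any bias cannot be computed.

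Four stronger conclusions may be tempting, but the documents do not support them:

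- *That the 80% adherence set is compromised through accountability adjudication.* Section 6.4 bases adherence on capsule counts and interviews. Bottles come back at the week-4 EGG visit (8.1.4) and adherence is reviewed at weeks 2 and 4 (1.3). No passage links the 80% classification to the adjudication in section 6.2.1, which may in any case be done during the trial.
- *That the harm could not be repaired.* Meal distribution is read from archived images, which masked readers could read again.
- *That all of exploratory outcomes 1 and 2 are at risk.* Water volume and the quantitative EGG measures are little exposed, and readings finished before release are not exposed at all.
- *That the secondary 2- and 4-hour retention results are affected.* The text does not say whether these are read centrally.

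**What to change.** **Section 6.3.** Replace the visit-based trigger with a lock-based one: treatment codes are released only after the 7-day and 30-day event windows have closed for all participants, all queries and any remaining drug accountability are resolved, and the database is locked. The existing provisions for emergency and individual unmasking are unaffected.

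**Section 9.4.9.** Add that any central meal-distribution or EGG reading completed after code release is made by readers who stay masked to treatment until their readings are locked. The same rule should cover baseline readings used for the fundic accommodation subgroup in section 9.4.7. The primary analysis then need not wait for the central readings.

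**Optional.** Readers could also be masked to visit order. That would need files to be de-identified and re-ordered, which is extra work, and the main correction does not depend on it.

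**Cost.** Two wording changes and a short delay in opening the codes: at least the 30 days of the last serious-event window (30/7 = 4.3 weeks, against a planned total of 137 weeks), plus whatever time the remaining queries take. Keeping late readers masked requires only that the codes be withheld from them.
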